6.4.3. Blinding of the Sponsor

As this is a sponsor-open study, the sponsor may conduct unblinded reviews of the data during the course of the study for the purpose of safety assessment, facilitating dose-escalation decisions, facilitating PK modeling, and/or supporting clinical development. Individual participant-level unblinded data will be reviewed by a designated limited number of sponsor personnel.

6.4.4. Sensitive Clinical Data

Sensitive clinical data are data collected in this study that have the potential to unblind a participant's treatment assignment. Access to sensitive clinical data will be restricted to authorized individuals until the study has been unblinded. The following data variables are considered sensitive clinical data:

- Study intervention assignments (PF-06954522 or placebo);
- Individual PF-06954522 PK data.

6.4.5. Breaking the Blind

The method for breaking the blind in this study will be manual. In case of an emergency, the investigator has the sole responsibility for determining if unblinding of a participant's treatment assignment is warranted. Participant safety must always be the first consideration in making such a determination. If the investigator decides that unblinding is warranted, the investigator should make every effort to contact the study medical monitor prior to

unblinding a participant's treatment assignment unless this could delay further management of the participant. If a participant's treatment assignment is unblinded, the sponsor must be notified within 24 hours after breaking the blind. When the blinding code is broken, the reason must be fully documented and entered on the CRF.

Blood specimens will be obtained from all participants for PK analysis to maintain the study blind at the investigator site. Only the investigator site staff and blinded study monitor, if assigned, will be blinded to study treatment. Other Pfizer personnel will be unblinded to participant treatments in order to permit real-time interpretation of the safety and PK data; and provide information necessary to potentially alter the dose escalation- sequence. The blinded study monitor, if assigned, will remain blinded to treatment until all monitoring for the study has been completed. Specimens from participants randomized to placebo will not be routinely analyzed. To minimize the potential for bias, treatment randomization information will be kept confidential by Pfizer unblinded personnel and will not be released to the blinded investigator or blinded investigator site personnel until the study database has been locked or the investigator requests unblinding for safety reasons.

6.5. Study Intervention Compliance

When the individual dose for a participant is prepared from a bulk supply, the preparation of the dose will be confirmed by a second qualified member of the study site staff.

When participants are dosed at the site, they will receive study intervention directly from the investigator or designee, under medical supervision. The date and time of each dose administered in the clinic will be recorded in the source documents and recorded in the CRF. The dose of study intervention and study participant identification will be confirmed at the time of dosing by a member of the study site staff other than the person administering the study intervention. Study site personnel will examine each participant's mouth to ensure that the study intervention was ingested.

6.6. Dose Modification

The decision to proceed to the next dose level of PF-06954522 (either an increase, decrease, or repeat of a previous dose level) will be made by the study team and the investigator based on observed safety, tolerability, and preliminary PK data obtained at the prior dose level. At least 8 and 6 participants (including at least 1 placebo participant) must complete the prior dose level in Cohort 1 and 2, respectively. PK data through at least 24 hours post-dose and safety and tolerability data through at least 48 hours post-dose of the current period will be reviewed. Cumulative safety and tolerability from all previous periods will also be reviewed.

The dosing schedule may also be adjusted to expand a dosing cohort to further evaluate safety, tolerability, and/or PK findings at a given dose level or to add cohorts to evaluate additional dose levels or repeat dose levels. The study procedures for these additional participant(s)/cohort(s) will be the same as that described for other study participants/cohorts unless otherwise indicated.

6.6.1. Dose Escalation and Stopping Rules

Dose escalation stopping rules will be used to determine whether the maximal tolerated dose has been attained. Dose escalation may be stopped if it is determined that the limits of safety and/or tolerability have been reached. This decision will be made after a discussion takes place between the sponsor study team and the investigator. The sponsor study team may not overrule the investigator's decision to stop dose escalation. If dose escalation is stopped because of any of these criteria, additional cohorts may receive the same or lower doses of the study intervention.

The dose escalation will be terminated based on the following criteria:

- If 50% or more of the participants receiving active drug at a given dose level (but not
 participants receiving placebo) develop similar clinically significant laboratory, ECG,
 or vital sign abnormalities, in the same organ class, indicating dose-limiting
 intolerance.
- Severe nonserious AEs, considered as, at least, possibly related to study intervention administration, in 2 participants at a given dose level (but not participants receiving placebo), independent of within or not within the same system organ class, indicating dose-limiting intolerance.
- Dosing will be paused for any SAE that occurs in a participant receiving active treatment until causality is fully assessed by the PI and sponsor. Dosing may resume if the SAE is determined to be not drug-related by the PI and sponsor. If the SAE is determined to be either drug-related or unknown, either dosing will cease or the SAE will be evaluated by the sponsor's protocol review committee (or similar review group), which is independent of the study team and investigators. If the protocol review committee determines that dosing may resume, a plan that mitigates risks to participants with the resumption of dosing will be implemented. Such a plan could include a revision of inclusion/exclusion criteria, repeating or reducing the dose, or adding appropriate safety monitoring.
- It is determined that the limit of safety and/or tolerability has been reached. This
 decision will be made following discussions between the study team and the
 investigator.
- Other findings that, at the discretion of the study team and investigator, indicate that dose escalation should be halted.
- If, at any dose level, the average exposure reaches or exceeds the PK stopping limits:
- If, based on the observed data, the group mean C_{max} or AUC (based on total plasma concentration) of the next planned dose is projected to exceed the escalation limits, that dose will not be explored. Modified doses may be explored if they are not expected to exceed PK stopping criteria.

The highest dose evaluated in this study will not exceed mg.

Progression to the next dose will occur if the last dose was well tolerated and after satisfactory review of the available safety and PK data.

6.7. Continued Access to Study Intervention After the End of the Study

No study intervention will be provided to participants at the end of their study participation.

6.8. Treatment of Overdose

For this study, any dose of PF-06954522 projected to result in exposures greater than the defined PK stopping limit of Section 6.6.1) within a 24-hour time period will be considered an overdose.

There is no specific treatment for an overdose.

In the event of an overdose, the investigator/treating physician should:

- 1. Contact the study medical monitor within 24 hours.
- 2. Closely monitor the participant for any AEs/SAEs and laboratory abnormalities as medically appropriate and follow up until resolution, stabilization, the event is otherwise explained, or the participant is lost to follow-up (as defined in Section 7.3).
- 3. Document the quantity of the excess dose as well as the duration of the overdose in the CRF.
- 4. Overdose is reportable to Pfizer Safety only when associated with an SAE.
- 5. Obtain a blood sample for PK analysis within 2 days from the date of the last dose of study intervention if requested by the study medical monitor (determined on a case-by-case basis).

Decisions regarding dose interruptions or modifications will be made by the investigator in consultation with the study medical monitor as needed based on the clinical evaluation of the participant.

6.9. Prior and Concomitant Therapy

Use of prescription or nonprescription drugs and dietary and herbal supplements are prohibited within 7 days or 5 half-lives (whichever is longer) prior to the first dose of study intervention with the exception of are prohibited within 14 days plus 5 half-lives prior to the first dose of study intervention (see Appendix 9).

Limited use of nonprescription medications that are not believed to affect participant safety or the overall results of the study may be permitted on a case-by-case basis following approval by the sponsor. Acetaminophen/paracetamol may be used at doses of ≤ 1 g/day.

Females taking hormone replacement therapy may be eligible to participate in this study if they are willing to discontinue therapy at least 28 days prior to the first dose of study treatment and remain off hormonal therapy for the duration of the study.

All concomitant treatments taken during the study must be recorded with indication, daily dose, and start and stop dates of administration. All participants will be questioned about concomitant treatment at each clinic visit.

Treatments taken within 28 days before the first dose of study intervention will be documented as a prior treatment. Treatments taken after the first dose of study intervention will be documented as concomitant treatments.

7. DISCONTINUATION OF STUDY INTERVENTION AND PARTICIPANT DISCONTINUATION/WITHDRAWAL

7.1. Discontinuation of Study Intervention

It may be necessary for a participant to permanently discontinue study intervention. Reasons for permanent discontinuation of study intervention include the following: AEs or other (administrative) reasons.

Discontinuation of study intervention does not represent withdrawal from the study. If study intervention is permanently discontinued, the participant should remain in the study to be evaluated for ongoing AEs. See the SoA for data to be collected at the time of discontinuation of study intervention and follow-up for any further evaluations that need to be completed.

In the event of discontinuation of study intervention, it must be documented on the appropriate CRF/in the medical records whether the participant is discontinuing further receipt of study intervention or also from study procedures, further study follow-up, and/or future collection of additional information.

7.1.1. Potential Cases of Acute Kidney Injury

Participants exposed to IMP demonstrating transient or sustained increase in Screat (with decrease in Screat-based eGFR or eCrCl) require expedited evaluation to differentiate AKI from DICI. DICI is defined as transporter-mediated effect related to altered renal tubular creatinine handling without histological injury.

AKI may be due to one or more types of injury, including DIKI. Differentiation of DIKI from other causes of AKI and from DICI may require clinical, radiographic, histopathologic, and laboratory assessments, as well as nephrology consultation.

Follow-up Assessments

The participant should return to the site for evaluation as soon as possible, preferably within 48 hours of awareness of the abnormal results.

Evaluation should include physical examination, laboratory tests, detailed medical and surgical history, review of all medications (including recreational drugs and supplements [herbal]), family history, sexual history, travel history, blood transfusion, and potential occupational exposure to chemicals.

Laboratory assessments should include simultaneous serum cystatin C (Scys) and serum creatinine (Screat) tests. Estimates of eGFR, eCrCl and Screat-based eGFR and combined Screat-Scys-based eGFR should also be derived using the appropriate equation described in Appendix 7.

Assessments of urine albumin-to-creatinine ratio or urine volume may also be performed as appropriate.

If appropriate, nephrology consultation may be recommended to facilitate differentiation of renal parenchymal disease, pre-renal azotemia, and post-renal obstruction.

Differentiating Acute Kidney Injury from DICI

A confirmed Screat increase is defined as:

- (i) $\geq 0.3 \text{ mg/dL}$ ($\geq 26.5 \mu \text{mol/L}$) within 48 hours OR
- (ii) confirmed Screat increase \geq 1.5 times baseline (known or suspected to have occurred within the prior 7 days).

Based on the assessments performed, suspected AKI (including DIKI) may be differentiated from DICI as follows.

Adult participants

	AKI (including DIKI) Any one of the below	DICI	
Scys & Screat	Simultaneous, confirmed serum cystatin C (Scys) increase and confirmed Screat increase	Confirmed Screat increase without confirmed increase in reflex Scys AND Confirmed Screat-based eGFR	
eGFR	Decrease in Screat-based eGFR and combined Screat-Scys-based eGFR (when available)	decrease without confirmed combined Screat-Scys-based eGFR decrease.	
Albuminuria or proteinuria	Confirmed albuminuria increase (see Appendix 7 for Grades A1 to A3 quantitation)		
Urine volume	Urine volume <0.5 mL/kg/h for 6 consecutive hours		

Regardless of the presence or absence of increase in Screat, DIKI and other causes of AKI may be suspected if either there is (i) new-onset or worsening albuminuria or proteinuria are detected.

All confirmed cases of clinically relevant decrease in kidney function should be considered potential cases of DIKI if no other reason for the kidney function abnormalities has been found.

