Hours After Dose			0	24	36	48	72			
Blinded study intervention administration			See Table 2							
Standardized meals/snack		X	X	↑	\rightarrow	→	X			See Section 5.3.2.
Blood sample for:										
Safety laboratory: hematology and chemistry	X	X		X			X	X		Participants must fast for ≥4 hours prior to any safety lab evaluation. See Section 5.3.2 for additional details. Day -1 results must be reviewed and confirmed acceptable prior to dosing.
Safety laboratory: calcitonin, amylase, lipase and total bile acids	Х	X		X			X	X		Participants must fast for ≥4 hours prior to any safety lab evaluation. For total bile acids, an 8-hour fasting is required. See Section 5.3.2 for additional details. Review of these data is not required prior to dose escalation; cumulative results will be reviewed as they become available.
Serum FSH	X									Only for postmenopausal women.
HbA1c, TSH, HBcAb, HBsAg, HBsAb, HCVAb and HIV	X									See Appendix 2: Clinical Laboratory Tests.
Retained Research Sample for Genetics (Prep D1)			X							Prep D1 Retained Research Samples for Genetics: If not collected on the designated collection day, collect at the next available time point when biospecimens are being collected in conjunction with a participant visit. Day 1 of Period 1 only
Retained Research Samples for Biomarkers [Prep B2.5]			See Table 2							To be collected as outlined in Section 8.7.2.

Table 1. Study Schedule of Assessments

Visit Identifier Abbreviations used in this table may be found in Appendix 10. Days Relative to							Day 4	F/U Visit	F/U Contact	•	Notes There are 5 periods in Cohort 1, 4 and 3 periods for optional Cohorts 2
Day 1	to Day -2	Day -1	Day 1	Da	.y 2	Day 3	Day 4	8-11	29-36		and 3, respectively. Follow-up contact may occur via telephone contact and must occur 28 to 35 days after administration of the final dose of study intervention.
Hours After Dose			0	24	36	48	72				
PF-06954522 PK blood sampling				X	X	X	X			X	See Section 8.5 for additional details.
CCI											
Urine sample for:											
Urine drug testing	X	X									Results of any pre-dose testing to be confirmed acceptable prior to dosing. Day -1 testing not required between study periods if participant remains in CRU.
Urinalysis (with microscopy, if needed)	X	X		X			X	X		X	
Urine albumin/creatinine ratio	X										

Table 2. Study Schedule of Assessments for PK, Vitals, and ECGs on Day 1 of Each Period

Visit Identifier Abbreviations used in					Per	iod 1 t	o Peri	od 5					Notes	

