- 8. Renal impairment as defined by an eGFR of <75 mL/min/1.73 m². Based upon participant age at screening, eGFR is calculated using the recommended CKD-EPI equations in Section 10.7.2 to determine eligibility (Screat-based formula) and to provide a baseline (Screat-Scys combined formula) to quantify subsequent kidney safety events. For eligibility assessment based upon estimated renal function, the higher of the screening and baseline eGFR values may be used.
- 9. Standard 12-lead ECG at Screening that demonstrates clinically relevant abnormalities that may affect participant safety or interpretation of study results (eg, QTcF >450 ms, complete LBBB, signs of an acute or indeterminate age myocardial infarction, ST-T interval changes suggestive of myocardial ischemia, second- or third- degree AV block, or serious bradyarrhythmias or tachyarrhythmias). If QTcF exceeds 450 ms, or QRS exceeds 120 ms, the ECG should be repeated twice and the average of the 3 QTcF or QRS values used to determine the participant's eligibility. Computer-interpreted ECGs should be overread by a physician experienced in reading ECGs before excluding a participant.
- 10. Participants with ANY of the following abnormalities in clinical laboratory tests at screening, as assessed by the study-specific laboratory and confirmed by a single repeat test, if deemed necessary:
 - ALT, AST, or bilirubin ≥1.05 × ULN. Participants with an elevated total bilirubin consistent with Gilbert's Disease may have a direct bilirubin measured and would be eligible for this study provided the direct bilirubin level is ≤ ULN;
 - TSH > ULN
 - HbA1c ≥6.5%;

- Hematuria as defined by $\geq 1+$ heme on urine dipstick;
- Albuminuria as defined by urine albumin/creatinine ratio (UACR) >30 mg/g.

Other Exclusion Criteria:

- 11. History of alcohol abuse or binge drinking and/or any other illicit drug use or dependence within 6 months of Screening. Binge drinking is defined as a pattern of 5 (male) and 4 (female) or more alcoholic drinks in about 2 hours. As a general rule, alcohol intake should not exceed 14 units per week (1 unit = 8 ounces (240 mL) beer, 1 ounce (30 mL) of 40% spirit, or 3 ounces (90 mL) of wine).
- 12. Use of tobacco/nicotine containing products in excess of the equivalent of 5 cigarettes/day or 2 chews of tobacco/day.

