10.7. Appendix 7: Kidney Safety: Monitoring Guidelines

10.7.1. Laboratory Assessment of Change in Kidney Function and Detection of Kidney Injury

Standard kidney safety monitoring requires assessment of baseline and postbaseline Screat measurement to estimate kidney function [eg, Screat-based eGFR]. Obtaining Screening or Baseline Scys and postbaseline reflex Scys (if confirmed Screat increase ≥0.3 mg/dL) makes it feasible to distinguish AKI from DICI. If Screat increase is confirmed after baseline, then reflex measurement of Scys is indicated:

ADULTS: Currently, 2021 CKD-EPI eGFR equations (Screat only-based and combined Screat plus Scys-based) are valid for use in adults only. At baseline Screat and Scys values are needed to calculate 2021 CKD-EPI eGFR by Screat only-based equation (see Section 10.7.2.1) and by combined Screat plus Scys-based equation. When post-baseline Screat increase ≥0.3 mg/dL is confirmed, then reflex Scys measurement is needed to enable post-baseline comparison of eGFR changes (Screat only-based eGFR and combined Screat plus Scys eGFR).

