10.7.2. Age-Specific Kidney Function Calculation Recommendations

10.7.2.1. Adults (18 Years and Above)—2021 CKD-EPI Equations

eGFR (mL/min/1.73m²)[17]

2021 CKD- EPI Screat Only	Screat (mg/dL)	Scys (mg/L)	Recommended eGFR Equation
Female	if ≤ 0.7	NA	$eGFR = 143 \times (Screat/0.7)^{-0.241} \times (0.9938)^{Age}$
Female	if > 0.7	NA	$eGFR = 143 \times (Screat/0.7)^{-1.200} \times (0.9938)^{Age}$
Male	if ≤ 0.9	NA	$eGFR = 142 \times (Screat/0.9)^{-0.302} \times (0.9938)^{Age}$
Male	if > 0.9	NA	$eGFR = 142 \times (Screat/0.9)^{-1.200} \times (0.9938)^{Age}$
2021 CKD-	Screat	Scys	Recommended eGFR Equation
EPI	(mg/dL)	(mg/L)	
Screat-Scys Combined			
Female	if ≤ 0.7	if ≤ 0.8	$eGFR = 130 \times (Screat/0.7)^{-0.219} \times (Scys/0.8)^{-0.323} \times (0.9961)^{Age}$
Female	if ≤ 0.7	if > 0.8	$eGFR = 130 \times (Screat/0.7)^{-0.219} \times (Scys/0.8)^{-0.778} \times (0.9961)^{Age}$
Female	if > 0.7	if ≤ 0.8	$eGFR = 130 \times (Screat/0.7)^{-0.544} \times (Scys/0.8)^{-0.323} \times (0.9961)^{Age}$
Female	if > 0.7	if > 0.8	$eGFR = 130 \times (Screat/0.7)^{-0.544} \times (Scys/0.8)^{-0.778} \times (0.9961)^{Age}$
Male	if ≤ 0.9	if ≤ 0.8	$eGFR = 135 \times (Screat/0.9)^{-0.144} \times (Scys/0.8)^{-0.323} \times (0.9961)^{Age}$
Male	if ≤ 0.9	if > 0.8	$eGFR = 135 \times (Screat/0.9)^{-0.144} \times (Scys/0.8)^{-0.778} \times (0.9961)^{Age}$
Male	if > 0.9	if ≤ 0.8	eGFR = $135 \times (\text{Screat}/0.9)^{-0.544} \times (\text{Scys}/0.8)^{-0.323} \times (0.9961)^{\text{Age}}$
Male	if > 0.9	if > 0.8	eGFR = $135 \times (\text{Screat}/0.9)^{-0.544} \times (\text{Scys}/0.8)^{-0.778} \times (0.9961)^{\text{Age}}$

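### The Section 7.1.1 table cannot separate a drug-induced creatinine increase (DICI) from acute kidney injury (AKI): with cystatin C unchanged, a creatinine rise always meets the AKI eGFR row

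*Protocol*

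**What the plan says.** Section 7.1.1 gives the mechanism: "DICI is defined as transporter-mediated effect related to altered renal tubular creatinine handling without histological injury". The laboratory pattern to expect is a creatinine rise with cystatin C unchanged.

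The table in that section has two columns. One AKI row suffices for the AKI column, and the eGFR row is "Decrease in Screat-based eGFR and combined Screat-Scys-based eGFR (when available". The DICI cell has two joint conditions: a confirmed creatinine increase without a confirmed increase in reflex cystatin C, and a confirmed creatinine-based eGFR "decrease without confirmed combined Screat-Scys-based eGFR decrease". Confirmed is given a size for creatinine (at least 0.3 mg/dL within 48 hours, or at least 1.5 times baseline) but none for eGFR or cystatin C. The text after the table adds that "All confirmed cases of clinically relevant decrease in kidney function should be considered potential cases of DIKI" if no other reason is found.

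Section 7.1.1 sends the calculation to Appendix 7, where Section 10.7.2.1 prints the 2021 CKD-EPI equations. Exclusion criterion 8 in Section 5.2 uses them "to provide a baseline (Screat-Scys combined formula) to quantify subsequent kidney safety events", although footnote a of Tables 5 and 6 only recommends a screening or baseline cystatin C.

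Section 10.7.1 has its own trigger, with no time window: "When post-baseline Screat increase ≥0.3 mg/dL is confirmed, then reflex Scys measurement is needed".

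**The concern.** The table exists to tell a benign effect on creatinine handling from injury, and cystatin C is the marker meant to do so. The AKI eGFR row and the second DICI condition instead rest on combined eGFR, which contains creatinine. If combined eGFR falls whenever creatinine rises, both cells respond to the very change they are meant to look past.

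Safety is the primary objective, and impaired renal function is listed in Section 2.3.1 as a potential class risk with eGFR surveillance as mitigation. About 8 participants receive active drug in each Cohort 1 period, so one wrongly labelled case is 1/8 = 12.5% of a dose group.

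**Working it through.** **Inputs.** The combined equations in Section 10.7.2.1 have these creatinine exponents:
- men: −0.144 up to 0.9 mg/dL, −0.544 above;
- women: −0.219 up to 0.7 mg/dL, −0.544 above.

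The cystatin C exponents are −0.323 up to 0.8 mg/L and −0.778 above. The creatinine rises are the two in 7.1.1. The baseline creatinine and cystatin C values, and age 40, are assumed values within eligibility (age 18 to 65, creatinine-based eGFR at least 75).

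**Step 1: sign.** With cystatin C fixed, its term and the age term cancel in the ratio of post-baseline to baseline combined eGFR. What remains is a creatinine term with a negative exponent, so the ratio is below 1 for any creatinine rise.

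**Step 2: size at a 1.5-fold rise.**
- Both values above the knot (0.9 men, 0.7 women): 1.5^−0.544 = 0.802, a fall of 19.8%.
- Men, both values at or below 0.9: 1.5^−0.144 = 0.943, a fall of 5.7%.
- Women, both values at or below 0.7: 1.5^−0.219 = 0.915, a fall of 8.5%.

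**Step 3: worked cases**, age 40, cystatin C 0.8 mg/L and unchanged. The last column is the cystatin C value that would be needed to keep combined eGFR at baseline.

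| Sex, creatinine (mg/dL) | Creatinine-only eGFR | Combined eGFR | Cystatin C needed |
|---|---|---|---|
| Man, 0.6 to 0.9 | 125.1 to 110.7 (−11.5%) | 122.4 to 115.5 (−5.7%) | 0.67 (−17%) |
| Man, 0.9 to 1.2 | 110.7 to 78.4 (−29.2%) | 115.5 to 98.7 (−14.5%) | 0.49 (−38%) |
| Man, 1.0 to 1.3 | 97.6 to 71.2 (−27.0%) | 109.0 to 94.5 (−13.3%) | 0.51 (−36%) |
| Man, 1.0 to 1.5 | 97.6 to 60.0 (−38.5%) | 109.0 to 87.5 (−19.8%) | 0.40 (−49%) |
| Woman, 0.5 to 0.75 | 120.9 to 102.6 (−15.1%) | 119.7 to 107.1 (−10.5%) | 0.57 (−29%) |
| Woman, 0.7 to 1.0 | 111.5 to 72.7 (−34.8%) | 111.2 to 91.6 (−17.6%) | 0.44 (−45%) |

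**Step 4: range.** I used both sexes, ages 18 to 65, baseline creatinine 0.40 to 1.40 mg/dL with creatinine-based eGFR at least 75, cystatin C 0.50 to 1.30 mg/L, and both rise sizes. Combined eGFR fell in all 231,370 combinations, by 5.7% to 19.8%.

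**Step 5: apply the table.** Both eGFRs fall, so the AKI eGFR row is met. Combined eGFR has decreased, so the DICI cell fails if any repeatable fall counts as confirmed. If confirmed meant a fall of more than about 20%, the DICI cell could be met at these rises. The AKI row carries no such word and would still be met, so the case would be in both columns. Larger rises also pass such a threshold: a doubling above the knot gives 1 − 2^−0.544 = 31.4%.

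**Step 6: the two creatinine triggers.** A rise from 0.50 to 0.75 mg/dL is 1.5-fold but only +0.25, so it meets 7.1.1 and not 10.7.1. Table 1 schedules "Safety laboratory: hematology and chemistry" on Day −1, at 24 hours and at 72 hours. The series 1.0, 1.15, 1.3 at those times gains 0.15 over the 48 hours from 24 to 72 hours, and 0.3 (1.3-fold) over about 4 days. It meets 10.7.1 and not 7.1.1.

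**The case against.** The strongest reply is that the table is an aid to triage. It separates suspected AKI, says cases may be differentiated this way, and allows clinical, imaging, histology and nephrology input. That stands: the investigator can still conclude DICI. To do so, however, they must set aside an AKI row that is met, on the one distinction the table is there to make. The qualifier in the AKI row for when combined eGFR is available does not help either. Without a combined value, the creatinine-only fall meets the row.

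Three stronger readings are tempting, and the documents do not support them.
- A reader might infer that DICI can never be returned. That goes too far, because confirmed is undefined for eGFR and a threshold could let the DICI cell be met alongside the AKI row. A large enough fall in cystatin C would also reach it.
- A reader might infer that benign cases will appear as AKI in the primary adverse event tables. Section 10.3.3 asks for a diagnosis where possible, and SAP 6.1.1 tabulates by preferred term. But in Section 10.7.4 AKI has no Grade 1 or 2 and starts where hospitalization is indicated, while increased creatinine has its own lower grades. The step from table row to event term is an inference.
- A reader might infer an effect on withdrawal or escalation. No rule in Sections 6.6.1 or 7.1 uses the AKI or DICI label.

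The difference between 7.1.1 and 10.7.1 also matters less than it looks. Footnote a of Tables 5 and 6 refers the cystatin C trigger to 7.1.1, whose work-up already asks for simultaneous cystatin C. Finally, the visible text reports no creatinine-transporter effect for this drug, although parts of Section 2.2 cannot be read, so how often such a case would arise is unknown.

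**Conclusion.** Wrong as written, and minor. With cystatin C unchanged, any creatinine rise meets the AKI eGFR row, and at the rises in 7.1.1 combined eGFR falls 5.7% to 19.8% from creatinine alone. Depending on how confirmed is read, the case is AKI only or both AKI and DICI, so the table does not separate the two. The sign follows from the printed equations and needs no assumption beyond unchanged cystatin C; the percentages rest on the assumed baseline creatinine values. The error is in the cautious direction, touches the case label only, and leaves the investigator's judgement in place.

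**What to change.** Suggested changes to Section 7.1.1 and Appendix 7:

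1. **AKI eGFR row.** *A fall in creatinine-based eGFR and in combined eGFR, with cystatin C above baseline on repeat testing. A combined-eGFR fall that creatinine alone explains does not by itself indicate AKI.*
2. **DICI cell.** Delete only the combined-eGFR clause and keep confirmed: *Confirmed creatinine increase and confirmed fall in creatinine-based eGFR, no confirmed rise in reflex cystatin C against a baseline cystatin C, and no AKI row met.* Confirmed should mean the same for cystatin C in both cells, namely seen again on repeat.
3. **No baseline cystatin C.** DICI cannot be assigned. Keep the AKI eGFR row as the protocol now has it and treat the case as suspected AKI, so that a missing baseline never turns a real injury into DICI.
4. **Reflex cystatin C.** Draw it when either rise is met: at least 0.3 mg/dL with no time limit (10.7.1), or the 7.1.1 definition, including 1.5 times baseline. Section 10.7.1 should not be narrowed to the 7.1.1 definition, because the series 1.0, 1.15, 1.3 would lose its explicit trigger.

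Check of the new wording, man aged 40, creatinine 1.0 to 1.5, baseline cystatin C 0.9 (combined eGFR 99.5), cystatin C results repeated and no other AKI row met:
- Cystatin C flat: 79.8 (−19.8%), now DICI.
- Cystatin C up 14%: 72.1 (−27.6%), still AKI.
- Cystatin C up 1.5-fold: 58.2 (−41.5%), still AKI.

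The cost is protocol wording, plus a repeat cystatin C in the few cases where the first is raised, which the word confirmed already implies. A cystatin C rise that recurs by chance would still place some DICI cases under AKI, which is the cautious direction.
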